## APPENDIX 4. SOLICITED ADVERSE EVENT (AE) INTENSITY GRADING

Adverse Event	Age	Intensity Grade	Parameter
Pain at injection site	< 6 years of age	0: None	-
		1: Mild	Minor reaction to touch
		2: Moderate	Cries/protests on touch
		3: Severe	Cries when limb is moved/spontaneously painful
	≥ 6 years of age	0: None	-
		1: Mild	Any pain neither interfering with nor preventing normal every day activities
		2: Moderate	Painful when limb is moved and interferes with every day activities

Document: CHAD3-004-EBO-Z\_Interim\_Final\_SAP\_v1\_0  
Author: Version PPD Number: 1.0 Version Date: 18APR2016

Template No: CS\_TP\_BS016 – Revision 3  
Effective Date: 01May2012

Reference: CS\_WI\_BS005

		3: Severe	Significant pain at rest. Prevents normal every day activities
Redness * at injection site	All		Record greatest surface diameter in mm
Swelling at injection site	All		Record greatest surface diameter in mm
Fever **	All		Record temperature in °C/°F
Fatigue	≥ 6 years of age	0: Normal	-
		1: Mild	Fatigue that is easily tolerated
		2: Moderate	Fatigue that interferes with normal activity
		3: Severe	Fatigue that prevents normal activity
Gastrointestinal symptoms (nausea, vomiting, diarrhoea and/or abdominal pain)	≥ 6 years of age	0: Normal	-
		1: Mild	Gastrointestinal symptoms that are easily tolerated
		2: Moderate	Gastrointestinal symptoms that interfere with normal activity
		3: Severe	Gastrointestinal symptoms that prevent normal activity
Headache	≥ 6 years of age	0: Normal	-
		1: Mild	Headache that is easily tolerated
		2: Moderate	Headache that interferes with normal activity
		3: Severe	Headache that prevents normal activity
Drowsiness	< 6 years of age	0: None	Behaviour as usual
		1: Mild	Drowsiness easily tolerated
		2: Moderate	Drowsiness that interferes with normal activity
		3: Severe	Drowsiness that prevents normal activity
Irritability/Fussiness	< 6 years of age	0: None	Behaviour as usual
		1: Mild	Crying more than usual/no effect on normal activity
		2: Moderate	Crying more than usual/interferes with normal activity
		3: Severe	Crying that cannot be comforted/prevents normal activity
Loss of appetite	< 6 years of age	0: None	Appetite as usual
		1: Mild	Eating less than usual/no effect on normal activity
		2: Moderate	Eating less than usual/interferes with normal activity
		3: Severe	Not eating at all

\* In case it is not possible to determine the extent of redness on darkly pigmented skin, it will be reported as uninterpretable on the Diary Card and in eSource.

Document: CHAD3-004-EBO-Z\_Interim\_Final\_SAP\_v1\_0  
Author: Version PPD Number: 1.0 Version Date: 18APR2016

Template No: CS\_TP\_BS016 – Revision 3  
Effective Date: 01May2012

Reference: CS\_WI\_BS005

\*\* Fever is defined as temperature  $\geq 37.5^{\circ}\text{C}$  /  $99.5^{\circ}\text{F}$ . The preferred route for recording temperature in this study will be axillary.

The intensity of local vaccination site redness/swelling will be scored as follows:

Age	Intensity Grade	Diameter Measurement (mm)
1 to 5 years of age	0: None	-
	1: Mild	> 0 to $\leq 10$
	2: Moderate	> 10 to $\leq 30$
	3: Severe	> 30
6 to 12 years of age	0: None	-
	1: Mild	> 0 to $\leq 20$
	2: Moderate	> 20 to $\leq 50$
	3: Severe	> 50
13 to 17 years of age	0: None	$\leq 20$
	1: Mild	> 20 to $\leq 50$
	2: Moderate	> 50 to $\leq 100$
	3: Severe	> 100

The intensity of fever will be scored as follows:

Age	Intensity Grade	Temperature Reading ( $^{\circ}\text{C}$ )
All	0: None	< 37.5
	1: Mild	$\geq 37.5$ to $\leq 38.5$
	2: Moderate	> 38.5 to $\leq 39.5$
	3: Severe	> 39.5

Document: CHAD3-004-EBO-Z\_Interim\_Final\_SAP\_v1\_0

Author: Version PPD Number: 1.0 Version Date: 18APR2016

Template No: CS\_TP\_BS016 – Revision 3

Reference: CS\_WI\_BS005

Effective Date: 01May2012

Copyright © 2012 Quintiles Transnational Corp. All rights reserved.

The contents of this document are confidential and proprietary to Quintiles Transnational Corp. Unauthorised use, disclosure or reproduction is strictly prohibited.

## APPENDIX 5. LABORATORY ASSESSMENTS

Category	Test	Reported Unit	Conversion Factor	SI Unit	Toxicity Grading
Haematology	Basophils	%	1	%	
	Basophils absolute	/mm 	0.001	10  /L	
	Eosinophils	%	1	%	
	Eosinophils absolute	/mm 	0.001	10  /L	
	Haemoglobin	g/dL	10	g/L	Haemoglobin
	Lymphocytes	%	1	%	
	Lymphocytes absolute	/mm 	0.001	10  /L	
	Mean cell volume	fL	1	fL	
	Monocytes	%	1	%	
	Monocytes absolute	/mm 	0.001	10  /L	
	Neutrophils	%	1	%	

Document: CHAD3-004-EBO-Z\_Interim\_Final\_SAP\_v1\_0  
Author: Version PPD Number: 1.0 Version Date: 18APR2016

Template No: CS\_TP\_BS016 – Revision 3  
Effective Date: 01May2012

Reference: CS\_WI\_BS005

	Neutrophils absolute	/mm 	0.001	10  /L	
	Platelets	/mm 	0.001	10  /L	Platelets
	Red blood cells	/mm 	0.000001	10  /L	
	White blood cells	x10  /μL	0.001	10  /L	White blood cells - decrease
Biochemistry	Alanine aminotransferase	U/L	1	U/L	Alanine aminotransferase increase by factor
	Creatinine	umol/L	1	umol/L	Creatinine
		mg/dL	88.4	umol/L	

## APPENDIX 6. LABORATORY TOXICITY GRADING

Category	Test (Unit)	Age	Gender	Grade			
				1	2	3	4
Haematology	Haemoglobin (g/dL)	≤ 12 years of age	Both	7.5 to 8.49	6.5 to 7.49	5 to 6.49	< 5
		> 12 years of age	Male	10 to 10.9	9 to 9.9	8 to 8.9	< 8
			Female	8.5 to 9.4	7.5 to 8.4	6.5 to 7.4	< 6.5

Document: CHAD3-004-EBO-Z\_Interim\_Final\_SAP\_v1\_0  
Author: Version PPD Number: 1.0 Version Date: 18APR2016

Template No: CS\_TP\_BS016 – Revision 3  
Effective Date: 01May2012

Reference: CS\_WI\_BS005

	Platelets (x10  /μL)	≤ 12 years of age	Both	75 to 99.999	50 to 74.999	25 to 49.999	< 25
		> 12 years of age	Both	75 to 100	50 to 74.999	25 to 49.999	< 25
	White blood cells - decrease (x10  /μL)	≤ 12 years of age	Both	2.5 to 3.999	1.50 to 2.499	1 to 1.499	< 1
		> 12 years of age	Both	2 to 2.749	1.50 to 1.999	1 to 1.499	< 1
Biochemistry	Creatinine (mg/dL)	≤ 12 years of age	Both	1.2 to 1.7	> 1.7 to 2.1	> 2.1 to 2.5	> 2.5
		> 12 years of age	Both	1.5 to 1.7	> 1.7 to 2	> 2.0 to 2.5	> 2.5
	Alanine aminotransferase increase by factor	≤ 12 years of age	Both	1.1 to 2.5xULN	> 2.5 to 5.0xULN	> 5.0 to 10xULN	> 10xULN
		> 12 years of age	Both	1.1 to 2.5xULN	> 2.5 to 5.0xULN	> 5.0 to 10xULN	> 10xULN

ULN: Upper limit of the normal range.

Note: acceptable limits for eligibility and grading scale adapted from Division of AIDS table for grading severity of adult and pediatric adverse events December 2004; WHO Toxicity Grading Scale for Determining Severity of Adverse Events, February 2003; Toxicity Grading Scale for Healthy Adult and Adolescent Volunteers Enrolled in Preventive Vaccine Clinical Trials, Guidance for Industry, 2007.

## APPENDIX 7. VITAL SIGNS ASSESSMENTS

Assessment	Unit
Temperature	C
Height	cm

Document: CHAD3-004-EBO-Z\_Interim\_Final\_SAP\_v1\_0  
Author: Version PPD Number: 1.0 Version Date: 18APR2016

Template No: CS\_TP\_BS016 – Revision 3  
Effective Date: 01May2012

Reference: CS\_WI\_BS005

Copyright © 2012 Quintiles Transnational Corp. All rights reserved.

The contents of this document are confidential and proprietary to Quintiles Transnational Corp. Unauthorised use, disclosure or reproduction is strictly prohibited.

---

Weight	kg
Heart rate	beats per minute
Respiratory rate	breaths per minute

---

Document: CHAD3-004-EBO-Z\_Interim\_Final\_SAP\_v1\_0  
Author: Version PPD Number: 1.0 Version Date: 18APR2016

Template No: CS\_TP\_BS016 – Revision 3  
Effective Date: 01May2012

Reference: CS\_WI\_BS005

---

## APPENDIX 8.      **PHYSICAL ASSESSMENTS**

Assessment
Abdomen
Anorectal
Breast
Cardiovascular
Eyes/Ears/Nose/Throat
Genitalia
Head/Neck/Thyroid
Lymph nodes
Musculoskeletal
Neurological
Respiratory
Skin

---

Document: CHAD3-004-EBO-Z\_Interim\_Final\_SAP\_v1\_0  
Author: Version PPD Number: 1.0 Version Date: 18APR2016

Template No: CS\_TP\_BS016 – Revision 3  
Effective Date: 01May2012

Reference: CS\_WI\_BS005

## MODIFICATION HISTORY

Unique Identifier for this Version	Date of the Document Version	Author	Significant Changes from Previous Authorised Version
1.0	18APR2016	PPD	Not Applicable – First Version

Document: CHAD3-004-EBO-Z\_Interim\_Final\_SAP\_v2\_0  
 Author: PPD Version Number: 2.0 Version Date: 14JUN2017

Template No: CS\_TP\_BS016 – Revision 3  
 Effective Date: 01May2012

Reference: CS\_WI\_BS005

2.0	14JUN2017	PPD	
Added the additional analysis as was prepared on an ad hoc basis for the interim analysis as well as some pooled tables and figures based on the additional analysis.
 
Added pregnancy summary.
 
Removed the anti-GP above threshold analyses.
 
Update the Quintiles logo to the QuintilesIMS logo.

-----	-----------	-----	--

Document: CHAD3-004-EBO-Z\_Interim\_Final\_SAP\_v2\_0  
Author: PPD Version Number: 2.0 Version Date: 14JUN2017

Template No: CS\_TP\_BS016 – Revision 3  
Effective Date: 01May2012

Reference: CS\_WI\_BS005

---

## 1. INTRODUCTION

This document describes the rules and conventions that will be used in the planned presentation and analysis of safety and immunology data for Protocol 202090 (EBOLA Z CHAD3-004) as set out in the latest version of the interim and final analysis table, listing and figure (TLF) shells. It describes the data that will be summarised and analysed, including specifics of the statistical analyses to be performed.

This statistical analysis plan (SAP) is based on:

- Amendment 2 Final version of the protocol, dated 06MAY2015.
- Addendum Ghana, dated 07AUG2015.
- Latest version of the analysis cohort assignment documentation.

This version of the SAP is focused on the safety and immunology data for the unblinded interim analysis as well as the final analysis.

## 2. STUDY OBJECTIVES AND ENDPOINTS

The following relates to the overall study objectives as described in Section 2: Objectives, of the protocol, as well as the overall study endpoints as described in Section 11: Statistical Methods, of the protocol.

### 2.1. PRIMARY OBJECTIVE AND ENDPOINTS

#### 2.1.1. PRIMARY OBJECTIVE

The primary objective is to assess the safety and reactogenicity of a single intramuscular dose of the ChAd3-EBO-Z vaccine:

- Overall.
- Separately in children aged:
  - o 1 to 5 years.
  - o 6 to 12 years.
  - o 13 to 17 years.

#### 2.1.2. PRIMARY ENDPOINTS

- Occurrence of each solicited local and general adverse event (AE), during a 7-day follow-up period after each vaccination (that is, the day of vaccination and 6 subsequent days), in all subjects, in both groups.
- Occurrence of any unsolicited AE, during a 30-day follow-up period after each vaccination (that is, the day of vaccination and 29 subsequent days), in all subjects, in both groups.
- Occurrence of haematological (complete blood count [CBC], including differential count and platelet count) and biochemical (alanine aminotransferase [ALT], creatinine) laboratory abnormalities at Screening, Day 3, Day 6, Day 30, Month 6, Month 6 + 6 days, Month 6 + 30 days and Month 12 in all subjects, in both groups.
- Occurrence of clinical symptoms of thrombocytopenia (AE of specific interest), during a 7-day follow-up period after vaccination at Day 0 (that is, Day 0 up to Day 6), in all subjects, in both groups.
- Occurrence of any serious adverse event (SAE), in all subjects, in both groups.

### 2.2. SECONDARY OBJECTIVE AND ENDPOINTS

#### 2.2.1. SECONDARY OBJECTIVE

The secondary objective is to assess the humoral immunogenicity of a single intramuscular dose of the ChAd3EBO-Z vaccine, in terms of anti-glycoprotein (GP) Ebola Virus Zaire (EBOV) antibody responses:

---

Document: CHAD3-004-EBO-Z\_Interim\_Final\_SAP\_v2\_0  
Author: PPD Version Number: 2.0 Version Date: 14JUN2017

Template No: CS\_TP\_BS016 – Revision 3  
Effective Date: 01May2012

Reference: CS\_WI\_BS005

- Overall.
- Separately in children aged:
  - o 1 to 5 years.
  - o 6 to 12 years.
  - o 13 to 17 years.

### 2.2.2. SECONDARY ENDPOINT

- Anti-GP EBOV antibody concentrations, as measured by enzyme-linked immunosorbent assay (ELISA):
  - o At Day 0 and Day 30, in all subjects, in both groups.
  - o At Month 6 and Month 6 + 30 days, in all subjects in the Group MENACWY-TT/EBO-Z.

## 2.3. TERTIARY OBJECTIVES AND ENDPOINTS

### 2.3.1. TERTIARY OBJECTIVES

The exploratory objectives are:

- To assess the persistence of the humoral immune response induced by a single intramuscular dose of the ChAd3-EBO-Z vaccine, in terms of anti-GP EBOV antibody responses:
  - o Overall.
  - o Separately in children aged:
    - 1 to 5 years.
    - 6 to 12 years.
    - 13 to 17 years.
- To assess EBOV-specific cell-mediated immunity (CMI) of a single intramuscular dose of the ChAd3-EBO-Z vaccine:
  - o Overall.
  - o Separately in children aged:
    - 1 to 5 years.
    - 6 to 12 years.
    - 13 to 17 years.
- To assess the pre-existing immunity to the ChAd3 virus vaccine vector prior vaccination, ChAd3-specific immune responses after vaccination and explore its potential impact on Ebola-specific immune responses:
  - o Overall.
  - o Separately in children aged:

Document: CHAD3-004-EBO-Z\_Interim\_Final\_SAP\_v2\_0

Author: PPD Version Number: 2.0 Version Date: 14JUN2017

Template No: CS\_TP\_BS016 – Revision 3

Reference: CS\_WI\_BS005

Effective Date: 01May2012

1 to 5 years.  
6 to 12 years.  
13 to 17 years.

- If deemed necessary, to further characterise the immune response to/the safety profile of the investigational ChAd3-EBO-Z vaccine.

### 2.3.2. TERTIARY ENDPOINTS

- Anti-GP EBOV antibody concentrations, as measured by ELISA:
  - o At Month 6 and Month 6 + 30 days, in all subjects, in the Group EBO-Z/MENAWY-TT.
  - o At Month 12, in all subjects, in both groups.
- Magnitude, responder rate and cytokine co-expression profile of ChAd3-EBO Z-specific CD4+ or CD8+ T-cell responses, as assessed by intracellular cytokine staining (ICS) after stimulation with EBOV GP antigens:
  - o At Day 0, Day 30, Month 6, Month 6 + 30 days and Month 12, in a sub-cohort of 30 subjects per age stratum, per group.
- ChAd3 neutralising antibody titres, as measured by a neutralisation assay:
  - o At Day 0, Day 30 Month 6 and Month 6 + 30 days, in a subset of 30 subjects per age stratum, per group.

## 3. STUDY DESIGN

### 3.1. GENERAL DESCRIPTION

A phase 2, randomised, observer-blind, controlled, multi-country study with two groups and three age strata as described below in Table 1: Treatment Groups:

Table 1: Treatment Groups

Treatment Group	Age Stratum	Number of Subjects	Treatment Name	
			Day 0	Month 6
EBO-Z/MENACWY-TT	13 to 17 years	~100	ChAd3-EBO-Z	Nimenrix
	6 to 12 years	~100		
	1 to 5 years	~100		

Document: CHAD3-004-EBO-Z\_Interim\_Final\_SAP\_v2\_0

Author: PPD Version Number: 2.0 Version Date: 14JUN2017

Template No: CS\_TP\_BS016 – Revision 3

Reference: CS\_WI\_BS005

Effective Date: 01May2012

Copyright © 2012 Quintiles Transnational Corp. All rights reserved.

The contents of this document are confidential and proprietary to Quintiles Transnational Corp. Unauthorised use, disclosure or reproduction is strictly prohibited.

	Total	~300		
MENACWY-TT/EBO-Z	13 to 17 years	~100	Nimenrix	ChAd3-EBO-Z
	6 to 12 years	~100		
	1 to 5 years	~100		
	Total	~300		

Randomised subjects will be followed for approximately 12 months from the Day 0 visit. Subjects will be randomised 1:1 to the two treatment groups. The randomisation will utilise stratification by age so that an equal number of children are randomised in each age stratum:

- 1 to 5 years.
- 6 to 12 years.
- 13 to 17 years.

In addition, the randomisation will utilise a minimisation procedure to account for the following factors:

- Gender.
- Centre (refer to Section 7.2: Multicentre Studies for details).

The study will have the following blinding implemented:

- Observer-blind:
  - o From study start until the interim analysis (refer to Section 4.2: Interim Analysis for additional information).
- Single-blind:
  - o From the interim analysis.

Additionally, a sub-selection of subjects will be enrolled into a sub-cohort:

- Sub-cohort for CMI, refer to Section 5.5.1: Sub-cohort for Cell-mediated Immunity (CMI for additional information).

The study design is presented below in Figure 1: Study Design Overview.

[figure not shown]
Figure 1: Study Design Overview

Document: CHAD3-004-EBO-Z\_Interim\_Final\_SAP\_v2\_0  
 Author: PPD Version Number: 2.0 Version Date: 14JUN2017

Template No: CS\_TP\_BS016 – Revision 3  
 Effective Date: 01May2012

Reference: CS\_WI\_BS005

**Rando** = randomisation; **yoa** = years of age; **Scr** = Screening; **D** = Day; **M** = Month; **BS (h/b)** = blood sample for haematology/ biochemistry parameters; **BS (I)** = blood sample for humoral immunity; **BS (CMI)** = blood sample for cell-mediated immunity.

Squares indicate visits to the vaccination centre. Rounded rectangles indicate study contacts (home visit or phone call).

**Yellow-coloured** visits indicate vaccination visits. At the Day 0 visit, subjects in the Group EBO-Z/ MENACWY-TT receive the investigational ChAd3-EBO-Z vaccine and subjects in Group MENACWY-TT/ EBO-Z receive *Nimenrix*. At the Month 6 visit, subjects in Group EBO-Z/ MENACWY-TT receive *Nimenrix* and subjects in the Group MENACWY-TT/ EBO-Z receive the investigational ChAd3-EBO-Z vaccine.

**Subjects will be followed-up for adverse events (AEs) on a daily basis during the 7-day follow-up period after vaccination (day 0 to 6). During this period, AEs will be recorded on a Diary Card. On those days that no study visit is planned, a home visit will be scheduled.**

† The Screening Visit and the Day 0 visit may take place on the same day (allowed interval 0 - 30 days).

\* Only for subjects in the sub-cohort for CMI.

\*\* IDMC review on all available safety data, which will include the safety data up to 7 days after vaccination at Day 0, from at least 50 children (25 per group) in an age stratum before proceeding to vaccination in the next (younger) age stratum (if applicable).

## 3.2. SCHEDULE OF EVENTS

Refer to Figure 1: Study Design Overview in the protocol, as well as Table 5: List of Study Procedures during Visits to the Vaccination Centre in the protocol.

## 3.3. CHANGES TO ANALYSIS FROM PROTOCOL

None.

Document: CHAD3-004-EBO-Z\_Interim\_Final\_SAP\_v2\_0

Author: PPD Version Number: 2.0 Version Date: 14JUN2017

Template No: CS\_TP\_BS016 – Revision 3

Reference: CS\_WI\_BS005

Effective Date: 01May2012

Copyright © 2012 Quintiles Transnational Corp. All rights reserved.

The contents of this document are confidential and proprietary to Quintiles Transnational Corp. Unauthorised use, disclosure or reproduction is strictly prohibited.

---

Document: CHAD3-004-EBO-Z\_Interim\_Final\_SAP\_v2\_0  
Author: PPD Version Number: 2.0 Version Date: 14JUN2017

Template No: CS\_TP\_BS016 – Revision 3  
Effective Date: 01May2012

Reference: CS\_WI\_BS005

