**(Amended 06 May 2015.)**

The percentage of subjects with at least one local AE (solicited and unsolicited), with at least one general AE (solicited and unsolicited) and with any AE during the solicited follow-up period will be tabulated with exact 95% CI. The same calculations will be performed for symptoms rated as Grade 3.

The percentage of subjects reporting each individual solicited local and general AE during the solicited follow-up period will be tabulated with exact 95% CI. The same tabulation will be performed for Grade 3 AEs and for AEs with relationship to vaccination.

Duration and prevalence of fever will be presented.

The verbatim reports of unsolicited symptoms will be reviewed by a physician and the signs and symptoms will be coded according to the Medical Dictionary for Regulatory Activities (MedDRA). The percentage of subjects with at least one report of unsolicited AE classified by the MedDRA and reported up to 29 days after vaccination will be tabulated with exact 95% CI. The same tabulation will be performed for Grade 3 unsolicited AEs and for unsolicited AEs with a relationship to vaccination.

At each haematology/ biochemistry sampling time point, by study group, individual haematological and biochemical values will be presented as number of subjects out of range (above and below normal range) and tabulated by toxicity grading (refer to [APPENDIX C](#)). In addition, changes from baseline (median/ interquartile range) will be presented.

SAEs *and AEs of specific interest (clinical symptoms of thrombocytopenia)* will be described in detail.

*(Amended 06 May 2015.)*

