## 11.11. Conduct of analyses

Any deviation(s) or change(s) from the original statistical plan outlined in this protocol will be described and justified in the final study report.

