### 3.3. CHANGES TO ANALYSIS FROM PROTOCOL

To be completed for the final analysis.

---

Document: CHAD3-004-EBO-Z\_Interim\_Final\_SAP\_v1\_0  
Author: Version PPD Number: 1.0 Version Date: 18APR2016

Template No: CS\_TP\_BS016 – Revision 3  
Effective Date: 01May2012

Reference: CS\_WI\_BS005

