All unsolicited AE incidence tables will include AEs reported during the collection period following the vaccination at Day 0. Therefore AEs reported during the collection period following the Month 6 vaccination will be excluded from the unsolicited AE incidence tables, unless otherwise specified.

All unsolicited AE incidence tables will be repeated for the following pooling of AEs, presented per age stratum:

- AEs following the active ChAd3-EBO-Z vaccination; hence:

- o EBO-Z/MENACWY-TT subjects: Unsolicited AEs within the reporting window following Day 0 vaccination.
- o MENACWY-TT/EBO-Z subjects: Unsolicited AEs within the reporting window following Month 6 vaccination.

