### 15.4. LABORATORY EVALUATIONS

Document: CHAD3-004-EBO-Z\_Interim\_Final\_SAP\_v2\_0  
Author: PPD Version Number: 2.0 Version Date: 14JUN2017

Template No: CS\_TP\_BS016 – Revision 3  
Effective Date: 01May2012

Reference: CS\_WI\_BS005

- 

The list of laboratory assessments to be included in the analysis is provided in APPENDIX 5: Laboratory Assessments.

The following listings are planned for presentation based on the Total Randomised Cohort:

- Clinical laboratory results, including change from Baseline and toxicity grading.
- Clinical laboratory results: Platelets, including an indication of subjects with AESIs.
- Malaria rapid diagnosis test (RDT) results.
- Pregnancy test results:
  - o Based on the Total Enrolled Cohort and only includes female subjects with results available.

The following tables are planned for presentation based on the Total Vaccinated Cohort:

- Clinical laboratory results, including change from Baseline:
  - o Descriptive statistics, including the interquartile range.Out of range clinical laboratory results:
  - o Number and percentage (%) of subjects with results above or below the normal range.
  - o Percentage (%) is relative to the number of subjects with result available for the specific test and the relevant time point.
- Toxicity grade shift from Baseline to post-baseline, the table will include the following categories:
  - o Grade 0. o Grade 1. o Grade 2. o Grade 3.
  - o Grade 4.
- Clinical Laboratory Percent Decrease from Baseline to Post-baseline: Platelets ( $10^9/L$ ):
  - o Number and percentage (%) of subjects with decrease in platelets in the derived categories will be summarized.
  - o Decrease in platelets from Baseline will be categorised as follows: Any increase
    - 0 to <10% decrease
    - 10% to <20% decrease
    - $\geq 20\%$  decrease o This table will be repeated for the maximum percent decrease observed between Day 3 and Day 6. o This table will not be repeated as a pooled table.
- Reported pregnancies per most recent vaccination and centre:
  - o The number and percentage (%) of reported pregnancies will be presented per most recent vaccination (Day 0 or Month 6) and centre as well as overall.
  - o The percentage will be based on the number of female subjects of childbearing potential within each centre.

All laboratory tables (unless otherwise noted) will be repeated for the following pooling of results:

---

Document: CHAD3-004-EBO-Z\_Interim\_Final\_SAP\_v2\_0

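### SAP v2 declares no changes from the protocol, yet it leaves AEs after Month 6 Nimenrix without an incidence table, omits the combined local and general AE rates, and alters the ChAd3 response rule

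*SAP*

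**What the plan says.** **Declaration.** Section 3.3 of the SAP is headed "CHANGES TO ANALYSIS FROM PROTOCOL". SAP v1 (18 April 2016) left it open: "To be completed for the final analysis". SAP v2 fills it with the single word None. Protocol 11.11 sets the standard: "Any deviation(s) or change(s) from the original statistical plan outlined in this protocol will be described and justified in the final study report".

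**AE tables.** Protocol 11.1 defines the solicited (7-day) and unsolicited (30-day) primary endpoints after each vaccination, in all subjects and both groups. SAP v2 section 15.1.2 limits the unsolicited incidence tables to the Day 0 period: "Therefore AEs reported during the collection period following the Month 6 vaccination will be excluded from the unsolicited AE incidence tables, unless otherwise specified". Section 15.2.2 does the same for solicited AEs. Both sections repeat the tables for pooled events after ChAd3-EBO-Z.

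**Combined rows.** Protocol 11.8 plans "The percentage of subjects with at least one local AE (solicited and unsolicited), with at least one general AE (solicited and unsolicited"), together with any AE, over the solicited follow-up period with exact 95% CIs, and again for Grade 3.

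**ChAd3 response.** Protocol Appendix A counts any post-vaccination increase as a positive response, excepting children already at the upper limit of quantitation (8748). SAP v2 section 14.1.2.1 requires a titre of at least 12 in baseline seronegatives or a 3-fold rise in seropositives, with no exception.

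**Additions and removals.** The v2 modification history reads: "Added the additional analysis as was prepared on an ad hoc basis for the interim analysis as well as some pooled tables and figures". It also records a pregnancy summary, a logo update and "Removed the anti-GP above threshold analyses". Among the additions is a platelet table in section 15.4: "Decrease in platelets from Baseline will be categorised as follows", with bands cut at 10% and 20%.

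**The concern.** Section 3.3 is where the author of the study report would look for departures to describe and justify. An entry of None there tells that author there are none.

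Two of the departures bear on primary safety endpoints, so they decide which results are tabulated as well as how the plan is documented. The third changes who counts as a responder on a tertiary endpoint.

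In a descriptive trial there is no alpha to protect. The main safeguard for a reader is being able to tell planned output from output prompted by the data. Platelet decreases are the reason that the protocol added its AE of specific interest, so the origin of the platelet table matters more than most.

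**Working it through.** The claim rests on no figure in the plan, so the check is a comparison of protocol Amendment 2, SAP v1 and SAP v2.

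**1. Which dose periods have an AE incidence table in v2?** Inputs: about 300 children per group (protocol 11.4), two doses each, so 600 × 2 = 1,200 planned doses.

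| Dose period | Planned doses | Main (Day 0) tables | Pooled tables |
|---|---|---|---|
| ChAd3-EBO-Z, Day 0 | ~300 | yes | yes |
| Nimenrix, Day 0 | ~300 | yes | no |
| ChAd3-EBO-Z, Month 6 | ~300 | no | yes |
| Nimenrix, Month 6 | ~300 | no | no |

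One dose period in four (300/1,200 = 25% of planned doses) has no stated incidence table for non-serious AEs. These events reach the listings only. SAEs are unaffected: section 15.1.5 tabulates them by dose, Nimenrix included. The exclusion ends with a proviso for tables specified otherwise, but nothing in the SAP body specifies one for Month 6 Nimenrix. Table 5 in v2 section 15.1.6 still gives a 30-day unsolicited window after each vaccination, so v2 is not consistent with itself.

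For scale, protocol Table 22 shows the precision that 300 doses would give. With Clopper-Pearson limits (lower = Beta quantile 0.025 with parameters x, n−x+1; upper = Beta quantile 0.975 with parameters x+1, n−x), n = 300 gives 0 to 0.0122 for x = 0 and 0.0283 to 0.0811 for x = 15, as printed.

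**2. Combined local and general rows.** Section 15.2.2 gives local and general rows for solicited AEs only. Section 15.1.2 has no local/general split, and section 15.3 combines solicited and unsolicited AEs only as any AE. The combined local and general percentages are therefore missing. The data exist: section 15.1 collects whether each unsolicited AE was at the administration site.

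**3. ChAd3 rule.** A baseline-seropositive child whose titre rises less than 3-fold is a responder under Appendix A and a non-responder under the SAP. If reported titres are capped at 8748 (an assumption), a 3-fold rise is impossible from any baseline above 8748/3 = 2916.

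**4. When did each item appear, and was it disclosed?**

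| Item | Protocol | SAP v1 | SAP v2 | v2 modification history |
|---|---|---|---|---|
| Month 6 AE exclusion | endpoints after each vaccination | not stated | stated | not mentioned |
| Combined local/general AE rows | planned | absent | absent | not mentioned |
| ChAd3 response | any increase, with exception | cut-off or x-fold, x open | cut-off or 3-fold | not mentioned |
| Anti-GP threshold analysis | not planned | conditional | removed | mentioned |
| Cytokine co-expression outputs | tertiary endpoint | no table listed | added | generic entry |
| Day 0 seropositive GMC table and curve; fever-onset and reactogenicity outputs; platelet percent-decrease table and box plot | not itemised | absent | added as planned | generic ad hoc entry |

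The history does not itemise the ad hoc outputs; the last two rows come from comparing v1 with v2.

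The list need not stop at three. The 5% trigger for repeating immunogenicity on the vaccinated cohort uses vaccinated subjects with serological results in protocol 11.9, but all subjects in a group in SAP section 14. With assumed counts of 300 vaccinated, 285 with serology and 14 of those excluded, the protocol gives 14/285 = 4.9% (no repeat) and the SAP (15 + 14)/300 = 9.7% (repeat).

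**The case against.** The other side has a good deal right.

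- **Two-step presentation.** Protocol 11.8 itself presents results by Day 0 treatment and then pools events after ChAd3-EBO-Z. V2 follows that order, and no ChAd3-EBO-Z event is lost from the incidence tables. This stands. It narrows the AE gap to Month 6 Nimenrix but does not close it, because 11.1 keeps both vaccinations in the endpoint.
- **Not post hoc.** The missing combined rows and the fold-based ChAd3 rule were already in v1, and v1 said that x would be fixed before the interim. This stands: a reader might infer that 3-fold was picked from the data, and nothing shows that. The protocol's rule also sits in an assay appendix, while 11.9 leaves vaccine response undefined. The two texts still differ and 3.3 is silent.
- **Anti-GP threshold.** It was never a protocol analysis and its removal is disclosed. It does not belong in 3.3.
- **Additions.** Co-expression serves a protocol tertiary endpoint. Several others extend planned summaries of fever, laboratory change and antibody distribution. The history openly calls the interim work ad hoc. That is disclosure of a kind, but the body lists each output as planned with no label.
- **Unseen shells.** The table shells might contain a by-dose table or the combined rows. They were not available, so absence here means absence from the SAP text.

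**Conclusion.** None in section 3.3 is wrong, and the consequence is moderate. One of four dose periods has no stated incidence table for non-serious AEs within the primary endpoints. One planned set of AE percentages is missing, and one tertiary response rule differs from the protocol. Only the first is new in v2, and the modification history does not record it.

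Three stronger readings are tempting and not supported:

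- That post hoc results will be reported as pre-specified. Protocol 11.11 still obliges the report to describe changes, and the history flags the ad hoc work, so this is a risk and not a certainty.
- That the platelet bands were chosen after unblinded data were seen. The documents date neither the interim nor the choice of bands. That v2 followed the interim is itself inferred from the history's past tense and from the requirement that the SAP be authorised beforehand.
- That error control is compromised. Protocol 11.11.2 and SAP section 7.4 state that there is no confirmatory objective, so no type I error claim arises.

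The conclusion assumes planned numbers of about 300 per group and that the SAP text reflects the tables to be produced.

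**What to change.** 1. Keep the Day 0 and pooled ChAd3-EBO-Z tables as protocol 11.8 sets out. Add a separate by-dose incidence table of solicited and unsolicited AEs after Month 6 Nimenrix, overall and by age stratum. Do not merge the two doses within a group, which would blur the Day 0 comparison.
2. Add rows for at least one local AE and at least one general AE, solicited and unsolicited combined, any grade and Grade 3, with exact 95% CIs, using the collected site-of-AE variable.
3. Replace None in 3.3 with each departure and its reason, including the ChAd3 response rule and its missing upper-limit exception, after a line-by-line comparison with the protocol. Record the Month 6 exclusion in the modification history.
4. Label the outputs first prepared ad hoc for the interim as not pre-specified, except the co-expression outputs.

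The cost is SAP wording, some title labels, one repeated set of AE tables and a few extra rows. No new data are needed: the SAP already derives dose at onset for both solicited and unsolicited AEs.
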